### *Secondary analyses*

Secondary outcome #1 (RADAR/DOOR) will be compared between treatment arms using Wilcoxon rank-sum test. Probability of a better RADAR/DOOR for a randomly selected patient using DETOURS strategy compared with control will be calculated, along with the 95% confidence interval.

Safety outcomes (secondary outcome #2) and process indicators (secondary outcome #3) will be analyzed using summary statistics.

Secondary outcomes including DOT and LOT (secondary outcomes #4, #5, and #6) will be analyzed using the same method as for the primary outcome #1 above.

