### 4.1.3 Treatment Assignment Procedures

Individual patients will be randomized to intervention or control (1:1). Participating sites will be provided site-specific randomization schema to ensure adequate representation of each arm within individual study sites.

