#### *Power calculations*

Power was calculated using a simulation study. First, we evaluated 6 months of data from three hospitals in our network, including 1 tertiary care center and 2 community hospitals. Eligible patients were defined as follows:

1. Blood cultures drawn and negative
  - a. Except 1 of 2 common skin flora
2. Broad antibiotics at 2-3 days after time of blood culture draw
3. We will define the 2nd calendar day after date of blood culture draw as “screen date”
4. The patient is eligible if they received broad antibiotic on either the screen date (day 2) or the day after (day 3).
5. Located on an inpatient medical, surgical, telemetry, or medical/surgical ward on screen date

The main outcome of interest was DOT after screen date, counting inpatient days of therapy occurring screen date + 1 until discharge, and adding post-discharge DOT as defined in electronic prescriptions upon hospital discharge. Table 4 outlines total enrollment assumptions at study hospitals.

A negative binomial regression model was fitted to the admission-level data on DOT. No difference in DOT was found between different types of wards (Medical/Surgical, Surgical, Medical and Telemetry;  $p=0.39$ ) so the final model included intercept only. Hospital was included as a random effect in the model. Mean DOT was estimated as  $\exp(\text{Intercept}) = \exp(2.43) = 11.4$  days, negative binomial scale as 1.68 and variance of the hospital random effect as 0.12.

**Table 4.** Total enrollment assumptions in 10 study hospitals.

		Enrollment/ month	Months in study	Enrollment estimate
Harvard	Academic	10	15	150
Duke	Academic	10	18	180
Penn	Academic	10	18	180
Presbyterian	Community	2	18	36
Wilson	Community	2	18	36
Iredell	Community	2	18	36
SRMC	Community	2	18	36
Fayette	Community	2	18	36
ATL	Community	2	18	36
Newnan	Community	2	18	36
			total	762

Power was estimated using a simulation study with 500 repetitions. Based on the above assumptions, DOT per admission in the standard care arm were generated in each hospital from a negative binomial distribution with mean=(11.4+hospital effect) and scale=1.68, where hospital effect was generated from a normal distribution with mean 0 and variance 0.12. DOT in the opt-out arm were generated from the same model with the mean=(eff\*11.4+hospital effect), where reduction in mean DOT parameter “eff” ranged in values from 0.9 to 0.6 (i.e. 10%-40% reduction).

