## 9.2 Randomization

Randomization will be performed using capabilities of the web-based RedCap system. Eligible patients will be randomized in a 1:1 ratio to intervention versus standard of care, with randomization stratified by hospital. Randomization scheme will be generated by the study statistician.

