## 9.4 Analysis Plan

### 9.4.1 Analysis

Descriptive data will be summarized by treatment group and overall using standard statistical methods. Full details of the planned analyses will be specified in a statistical analysis plan (SAP) which will be completed prior to the database lock.

*Primary analyses*

The primary outcome (antibiotic DOT) will be evaluated using GEE negative binomial regression with treatment as the only covariate, hospital as the cluster variable and assuming compound symmetry covariance structure within the clusters. Model fit will be examined and alternative distributions for the regression model (Poisson or overdispersed Poisson) may be considered.

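### DOOR/RADAR is to be compared by an ordinary Wilcoxon test and interval that do not reflect the hospital-stratified randomisation: valid, mildly conservative, and cheap to align

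*Protocol*

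**What the plan says.** Protocol section 9.2 has patients "randomized in a 1:1 ratio to intervention versus standard of care, with randomization stratified by hospital". Section 4.1.3 agrees: "Participating sites will be provided site-specific randomization schema".

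The primary DOT analysis in section 9.4.1 is a "GEE negative binomial regression with treatment as the only covariate, hospital as the cluster variable". The secondary DOT and LOT outcomes (numbers 4 to 6) use the same method, so they also account for hospital.

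DOOR/RADAR (secondary outcome 1) is treated differently. It "will be compared between treatment arms using Wilcoxon rank-sum test". The probability that a randomly chosen intervention patient does better than a control patient "will be calculated, along with the 95% confidence interval". Hospital appears in neither statement. Safety and process outcomes get summary statistics only, so among the secondary outcomes compared by a formal method DOOR/RADAR is the only one described without hospital.

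On how far hospitals differ, the power section reports, for DOT: "Hospital was included as a random effect in the model", with "negative binomial scale as 1.68 and variance of the hospital random effect as 0.12". It gives no power, event rate or between-hospital variation for DOOR, and leaves DOOR/RADAR power to be calculated later.

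**The concern.** When patients are randomised within hospital, each hospital has nearly equal arms, and differences between hospitals largely cancel from the treatment comparison. The ordinary rank-sum variance is computed as if all 762 patients had been randomised in one pool, so it still counts between-hospital variation that the design has removed. Where hospitals differ, that variance is too large, the p-value is a little too high and the interval a little too wide.

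At stake is a small amount of power and interval width on the leading secondary endpoint, and consistency between this analysis, the randomisation and the other modelled outcomes. The type I error rate is not at stake.

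**Working it through.** **Inputs from the protocol.** Ten hospitals with planned enrolment 150, 180, 180 and seven of 36 (150 + 180 + 180 + 7 × 36 = 762); 1:1 within hospital; control mean DOT 11.4; negative binomial dispersion 1.68; hospital variance 0.12; 25% reduction in mean DOT.

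**Assumptions not in the protocol.** Two-sided alpha 0.05 (inferred from the 95% interval); DOOR event rates of 15-40% and their split over ranks 2 to 6; no treatment effect on the DOOR rank itself; DOT as tie-break within a rank; hospital log-odds variance for DOOR of 0 to 0.25.

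**1. Reproducing the protocol's power.** Following its recipe (hospital effect added to the mean, GEE negative binomial, exchangeable correlation, 2,500 repetitions), power was 86.2% for a 25% reduction against 87% stated, 27.4% against 28% for 10%, and 95.8% against 96% for 30%. The 20% row gave 72.2% against 66%, which does not bear on this point. The DOT inputs are therefore read correctly.

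**2. What a variance of 0.12 means.** The SD is √0.12 = 0.346.
- Added to the mean, as in the protocol's simulation: hospital means one SD either side are 11.4 ± 0.35, or 11.05 to 11.75 DOT. Hospitals hardly differ.
- On the log scale, as in the fitted model: 11.4 × exp(±0.346), or 8.1 to 16.1 DOT. Hospitals differ appreciably.

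**3. Analytic size of the effect.** Let ρ be the share of rank variance lying between hospitals. Chance alone gives 9/761 = 1.2%. The excess that stratification can remove is e = (ρ − 9/761)/(1 − 9/761), and the standard error shrinks by the factor √(1 − e). On the log-scale reading, simulated ρ was about 2-5%.
- ρ = 0.02: e = 0.0083; interval 0.4% narrower; power of 80% becomes Φ(2.802/√0.9917 − 1.960) = 80.3%.
- ρ = 0.05: e = 0.0386; interval 1.95% narrower; power of 80% becomes 81.5%.

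**4. Is the pooled estimate itself noisier?** With 381 per arm and ignoring ties, the ordinary Wilcoxon standard error of the probability is √[763/(12 × 381 × 381)] = 0.0209. Applying step 3, the true value should be about 0.0205 to 0.0208. The simulated SD of the pooled estimate was 0.0203-0.0210, against 0.0206-0.0211 for the van Elteren version. The estimate loses nothing; the nominal variance is slightly too large.

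**5. Simulated power for DOOR/RADAR.**

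| Hospital effect on DOT | Unstratified | van Elteren | Gain (points) |
|---|---|---|---|
| 0.12 added to the mean, 25% reduction | 28.7% | 28.6% | none |
| 0.12 log scale, 25% reduction, event rates 15-40% (two examples) | 27.1%; 39.8% | 28.6%; 41.2% | 0.7 to 1.6 over the range |
| 0.12 log scale, 25% event rate, 25% reduction | 26.8% | 27.7% | 0.9 |
| 0.12 log scale, 25% event rate, 30% reduction | 36.0% | 37.1% | 1.1 |

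The first two rows use 4,000 trials per setting, the last two 3,000. A further run of 4,000 trials per setting at a 25% event rate gave about 0 on the additive reading and gains of 1.1 to 2.1 points (standard error about 0.3) on the log-scale reading. Under the null the unstratified test rejected in 4.5-5.7% of trials in every scenario.

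**The case against.** The strongest reply is that this belongs to the SAP. Section 9.4.1 defers full details to a plan that is not at hand, and the protocol does not say that the test is unstratified. That stands in part: the SAP may already name hospital strata. But the protocol does more than stay silent. It names the test and the effect measure, and as named these are the ordinary versions.

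A second reply is that the gain is nil to trivial on the protocol's own figures. That is right about size and is why this is a minor point. The 0.12 also describes DOT, not DOOR, for which nothing is given.

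A third is that stratifying has a price. That stands. A weighted average of within-hospital probabilities is not quite the pooled probability for a randomly selected patient, and its value depends on the weights. Seven strata are planned at only 36 patients.

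A reader might infer that hospital differences enter the pooled comparison as noise and blur the estimate, or that the test is invalid. Neither is supported: balance within hospitals already protects the estimate, and type I error stays near 5%. Nor do the documents support a large loss. Power rose from 21.1% to 28.9% only in a stress case (DOT variance 0.5, DOOR log-odds variance 1.0) well beyond anything the protocol reports.

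**Conclusion.** The point holds as a minor one. The DOOR/RADAR test and interval, as written, do not match the randomisation or the handling of hospital in the other modelled outcomes, and are mildly conservative as a result. The loss is nil on the additive reading of the hospital effect and about 1-2 power points on the log-scale reading, or an interval roughly 0.4-2% wider than it need be. These sizes depend on the assumed event rates, alpha and tie-break. The reason to change is that the analysis should follow the design at almost no cost. No conclusion of the trial is put at risk by leaving it.

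**What to change.** In section 9.4.1, or in the SAP before database lock, state that DOOR/RADAR is tested with a hospital-stratified Wilcoxon (van Elteren) test. For the effect measure choose one of two:

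- keep the pooled probability and compute its interval with a variance that respects the hospital strata. This leaves the stated estimand unchanged; or
- report a weighted average of within-hospital probabilities, with the weights fixed in advance and the change of estimand acknowledged.

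The cost is a sentence or two, standard software and no new data. Two limits should be accepted openly. Strata planned at 36 patients carry little information individually, and a hospital that ends with patients in only one arm contributes nothing to the stratified test. If the pooled probability is kept beside a van Elteren test, the two can disagree at the margin, so the text should say which is decisive.

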### 2.2 Scientific Rationale

Though intended to improve outcomes, some process measures lead to adverse outcomes, including unnecessary antibiotic use and increased rates of *C. difficile*. Similar concerns have been raised regarding the SEP-1 Core Measure. Yet, the risk of excess antibiotic use from SEP-1 has not been addressed.

Similarly, novel strategies to improve de-escalation of antibiotic therapy after initiation for suspected sepsis are warranted, but analyses of antimicrobial stewardship interventions are hampered by numerous methodological challenges. As a result, the NIAID’s Antibacterial Resistance Leadership Group (ARLG) recently proposed a new paradigm for evaluating risks and benefits in trials of stewardship interventions. This novel methodology, termed Desirability of Outcomes Ranking (DOOR)/Response Adjusted for Duration of Antibiotic Risk (RADAR), can better determine the impact of strategies to simultaneously reduce excess antibiotic exposures and improve patient outcomes.

Our **long-term goal** is to identify effective antimicrobial stewardship strategies that improve patient outcomes and decrease the risk of multidrug-resistant organisms (MDROs) and healthcare-associated infections (HAIs). The **overall objective** of this proposal is to develop and determine the efficacy of an opt-out protocol for antibiotic de-escalation on rates of antibiotic utilization and DOOR among qualifying non-ICU patients with suspected sepsis. We will achieve this objective by using the strengths of the Duke-UNC Prevention Epicenter, the Duke Antimicrobial Stewardship Outreach Network (DASON), and the Washington University and University of Pennsylvania Prevention Epicenters. This collaborative investigation will capitalize on our collective expertise in stewardship research and practice, expertise in and infrastructure for clinical trials, and robust data sources and analytics. Our **central hypothesis** is that use of an opt-out protocol for antibiotic de-escalation in qualifying non-ICU patients will lead to decreased antibiotic use and improved patient outcomes compared to control patients.

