###### *Secondary Hypothesis*

1. Patients in the intervention arm will have a 50% probability of a better DOOR compared to control patients.
2. Patients in the intervention arm will have reduced antibiotic-related adverse events, including *C. difficile* infection, compared to control patients.
3. Patients in the intervention arm will have equivalent rates of negative clinical outcomes such as mortality, length of stay, and subsequent ICU transfer compared to control patients.

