##### **3.1.3 Secondary Objectives**

To determine if the DETOURS opt-out protocol for antibiotic de-escalation will lead to improvement in DOOR among eligible patients identified with suspected sepsis.

To determine if the DETOURS opt-out protocol for antibiotic de-escalation will lead to reduction in *C. difficile* infections among eligible patients identified with suspected sepsis.

To determine if the DETOURS opt-out protocol for antibiotic de-escalation will lead to change in patient outcomes among eligible patients identified with suspected sepsis, including in-hospital mortality, length of stay, and subsequent ICU transfer compared to eligible patients in control units.

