**Table 3. DETOURS Desirability of Outcome Ranking (DOOR) Outcome**

Outcome	Rank
Alive	1
Readmission, relapse of suspected sepsis, C. difficile infection, OR deep venous thrombosis	2
≥2 of items in Rank 2 above	3
Subsequent ICU Admission OR hemodialysis	4
Subsequent ICU Admission AND hemodialysis	5

Death	6
-------	---

*Secondary endpoints:*

- 1) DOOR/RADAR, according to criteria developed in DETOURS-Retro (Pro00076818; Table 3). See Section 7 for definitions of these and other outcomes.
- 2) Safety outcomes potentially related to antibiotic treatments:
  - a. Individual clinical outcome components in the DOOR (Table 3)
  - b. Number of hospital days within 30-days post-randomization
  - c. Re-initiation of antibiotic therapy after >48 hours of no antibiotics within 30-days post-randomization
  - d. Need for new PICC line insertion within 30-days post-randomization
  - e. Central line days within 30-days post-randomization.
- 3) Process indicators:
  - a. Percent of eligible patients with antibiotic de-escalation by day 5, according to an electronic definition of de-escalation
  - b. Of those patients eligible for assessment of de-escalation per the Safety Checklist:
    - i. Number of eligible patients in whom the safety screen was applied.
    - ii. Number patients the safety screen excluded from the opt-out procedure
    - iii. Number of eligible patients in whom the opt-out procedure was employed
    - iv. Number of eligible patients in whom the prescriber chose to opt-out
      1. Prescriber type (e.g. physician, APC, trainee, specialty service consultant (e.g. infectious diseases))
      2. Prescribers' reported rationale for opting out
  - c. Percent of subjects who received an infectious disease consultation after implementation of the Opt-Out
- 4) Days of therapy for specific sub-groups of patients, including patients whose physicians elected to opt-out of the intervention, and sub-groups of hospitals (e.g., community vs. tertiary care hospitals).
- 5) Total days of therapy for each patient, defined as a sum of inpatient days of therapy and projected outpatient days of therapy, as per discharge prescriptions.
- 6) Length of therapy (LOT), defined as the number of days during which the patient receives one or more antibiotics. Repeat primary outcome and secondary outcomes #4 and #5 with LOT.

*Additional Descriptive Data*

We will obtain the following data from each of the patients eligible for the Opt-out protocol:

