## 7 ASSESSMENT OF SAFETY

All randomized patients will undergo safety evaluation.

1. Specifications of safety parameters –Data will be collected on the adverse outcomes described in the Desirability of Outcome Ranking (DOOR) in Table 3 and three other safety outcomes:
  - a. C. difficile infection (CDI) – positive *C. difficile* stool test during the 30 days following randomization. Results from either PCR or ELISA tests are acceptable
  - b. Clinically significant deep venous thrombosis (DVT) – diagnosis of a new DVT during the 30 days following randomization that requires anticoagulation. A radiographic finding (via ultrasound, CT, or MRI) will be required for this diagnosis.
  - c. Readmission – return to the hospital within 30 days of hospital discharge
  - d. Relapse of suspected sepsis – restart or escalation of antibiotic therapy coupled with repeat blood cultures (+/- 24 hours of changed in antibiotic therapy) during the 30 days following randomization.
  - e. Acute kidney injury requiring hemodialysis – new onset acute kidney injury requiring 1 or more hemodialysis sessions during the 30 days following randomization.
  - f. Transfer to Intensive Care Unit (ICU) – admission or transfer to any intensive care unit within 30 days of randomization.
  - g. Death – within 30 days of randomization.
  - h. Number of hospital days (Length of Stay) starting on the day of randomization and up to 30 days post randomization.
  - i. Re-initiation of antibiotic therapy after >48 hours of no antibiotics within 30 days of randomization.
  - j. Need for new PICC line insertion within the 30 days of randomization.
2. Methods and timing for assessing, recording, and analyzing safety parameters – Local study personnel will be responsible for assessing and recording safety parameters. Duke study personnel will be responsible for monitoring safety through interaction with study site PIs and the Independent Monitor.
3. Guidelines for determining causality – causality will not be assessed, as the DOOR outcome is intended to reflect global patient outcomes.
4. Reporting procedures (for AE) – all safety parameters will be entered into the REDCap database. Data on safety parameters will be reviewed by the Independent Monitor and discussed with the central study team.

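### The first secondary objective is about DOOR, but the only planned test and confidence interval are for DOOR/RADAR, which by its name also reflects antibiotic duration

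*Protocol*

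**What the plan says.** **Objective and hypothesis.** Protocol Section 3.1.3 asks whether the opt-out protocol "will lead to improvement in DOOR among eligible patients identified with suspected sepsis". Secondary hypothesis 1 in Section 3.1.1 is also on DOOR: "Patients in the intervention arm will have a 50% probability of a better DOOR compared to control patients". (As worded, 50% is the no-difference value of this statistic; I take the intent to be more than 50%.)

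**Definition of DOOR.** Table 3 in Section 5.1 has six ranks, from alive (1) to death (6). They are built from readmission, relapse of suspected sepsis, *C. difficile* infection, deep venous thrombosis, ICU admission, hemodialysis and death. No rank refers to antibiotics. Section 7 describes DOOR in the same spirit: "causality will not be assessed, as the DOOR outcome is intended to reflect global patient outcomes".

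**Endpoint and analysis.** Secondary endpoint 1, listed under that table, is "DOOR/RADAR, according to criteria developed in DETOURS-Retro". Section 9.4.1 then states: "Secondary outcome #1 (RADAR/DOOR) will be compared between treatment arms using Wilcoxon rank-sum test". It adds the estimate: "Probability of a better RADAR/DOOR for a randomly selected patient using DETOURS strategy compared with control will be calculated", with a 95% confidence interval. The individual DOOR components are secondary endpoint 2a and get summary statistics.

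**Meaning of RADAR.** Section 2.2 spells out the acronym as "Response Adjusted for Duration of Antibiotic Risk (RADAR") and says the method assesses strategies to "simultaneously reduce excess antibiotic exposures and improve patient outcomes". No section says how antibiotic duration enters the ranking. The labels DOOR, DOOR/RADAR and RADAR/DOOR are used without being distinguished.

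**The concern.** The objective names a clinical outcome. The endpoint and its only inference use a score that, by its name and stated purpose, also rewards shorter antibiotic exposure. An SAP that follows Section 9.4.1 as written would leave the Section 3.1.3 objective without an estimate or an interval.

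The difference matters in this trial because the intervention acts directly on antibiotic days, and DOT is the primary endpoint. Whatever part of DOOR/RADAR comes from antibiotic duration repeats the primary result. Enrolled patients have passed the Safety Check and Section 7 calls them low risk, so many pairs of patients may share a clinical rank. The antibiotic term would then decide those pairs. A DOOR/RADAR value above 50% could be read as support for the central hypothesis of improved patient outcomes (Section 2.2) when only DOT has changed.

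**Working it through.** **1. Fixing the DOT model.** Section 9.1 gives a negative binomial with mean 11.4 and scale 1.68, a hospital effect of variance 0.12, N = 762 and 87% power for a 25% reduction. I simulated this with the Table 4 hospital sizes, an additive hospital effect, two-sided alpha 0.05 (assumed), a log-ratio Wald test with cluster-robust variance, and 6,000 repetitions.
- 1.68 as dispersion (variance = μ + 1.68μ²): power **86.9%**, matching the stated 87%.
- 1.68 as size parameter: over 99%, which does not match.
- Other rows under the dispersion reading: 31%, 70%, 96% and over 99%, against the stated 28%, 66%, 96% and over 99%.

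The dispersion reading is used below.

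**2. Assumptions the protocol does not supply.**
- Antibiotic duration breaks ties in Table 3 rank, with fewer DOT better.
- DOT is independent of rank, has no 30-day cap, and (in this step) no hospital effect.
- Rank frequencies: the share in Rank 1 is varied from 60% to 80%.
- There are 762/2 = 381 patients per arm.

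**3. Formulas.** Let w = P(fewer DOT) + ½P(equal DOT), intervention against control. Then
- P(better DOOR) = P(win on rank) + ½ × P(rank tie)
- P(better DOOR/RADAR) = P(win on rank) + w × P(rank tie)

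Under the DOT model, w = 0.550 at a 25% reduction and 0.587 at 40%.

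**4. No clinical difference.** Worked case, ranks 1 to 6 at 75/16/3/3/0.5/2.5% in both arms:
- P(rank tie) = 0.75² + 0.16² + 0.03² + 0.03² + 0.005² + 0.025² = 0.591
- P(win) = (1 − 0.591)/2 = 0.205
- P(better DOOR) = 0.205 + 0.5 × 0.591 = 0.500
- P(better DOOR/RADAR), 25% reduction = 0.205 + 0.550 × 0.591 = **0.529**
- P(better DOOR/RADAR), 40% reduction = 0.205 + 0.587 × 0.591 = **0.552**

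The standard error is √((1/12)(2/381)) = 0.0209. The chance of significance in favour is Φ((P − 0.5)/0.0209 − 1.96), about 29% at a 25% reduction and 69% at 40%.

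Over the range of Rank 1 shares (simulated Wilcoxon tests, 2,000 repetitions):

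| Rank 1 share | 25% reduction | 40% reduction |
|---|---|---|
| 60% | 0.521 (19% significant) | 0.537 (43%) |
| 70% | 0.526 (24%) | 0.546 (61%) |
| 80% | 0.533 (36%) | 0.557 (80%) |

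DOOR alone is significant in favour in about 2.5% of these trials, as it should be.

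**5. Clinical harm.** Control ranks as in step 4; intervention ranks 70/18/3.5/3/0.5/5%, so event-free falls from 75% to 70% and deaths rise from 2.5% to 5%.
- P(win) = 0.194 and P(rank tie) = 0.557
- P(better DOOR) = 0.194 + 0.5 × 0.557 = **0.47**
- P(better DOOR/RADAR), 25% reduction = 0.194 + 0.550 × 0.557 = **0.50**; significantly better in about 3% of trials
- P(better DOOR/RADAR), 40% reduction = 0.194 + 0.587 × 0.557 = **0.52**; about 18%

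For DOOR alone, the tie-corrected standard error is 0.0209 × √(1 − 0.386) = 0.0164, where 0.386 is the sum of the cubed pooled rank shares. The chance of finding it significantly worse is Φ(0.0272/0.0164 − 1.96), about 38%.

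**6. Break-even at a 25% reduction.** Over the same range of Rank 1 shares, moving 3.0 to 5.2 percentage points from Rank 1 to death, or 4.8 to 6.6 points from Rank 1 to Rank 2, is the most that still leaves DOOR/RADAR at or above 0.50. P(better DOOR) is then 0.47 to 0.48.

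**The case against.** - **DOOR/RADAR is a deliberate, disclosed choice.** Sections 2.2, 2.3.2 and 11 present it as such, and Section 11 allows that limitations may be found. That stands, and it is a reason to keep DOOR/RADAR. It does not supply an analysis for an objective worded on DOOR.
- **Full analysis details are left to the SAP.** True, but the protocol itself fixes the objective on one quantity and the test on another. That is an inconsistency in this document and not a detail left for later.
- **The tie-break rule is not in the protocol.** This stands. Criteria are referred to DETOURS-Retro, and the rule used above is inferred from the name and stated purpose. Every number depends on it.
- **Rank frequencies are assumed.** This also stands. Rank 2 includes readmission within 30 days of discharge and relapse of suspected sepsis, so a high Rank 1 share cannot be taken for granted.
- **Clinical outcomes are not hidden.** Correct. Each component is a named endpoint with summary statistics, and the events are tabulated by arm for the Independent Monitor (Appendix 4). What is missing is an inferential summary of the six ranks.

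A reader might infer that a harmful intervention would often be declared significantly better. That follows only if 1.68 is read as the size parameter. At a 40% reduction w is then 0.654, the harm case gives 0.194 + 0.654 × 0.557 = 0.56, and about 80% of trials are significant in favour. That reading contradicts the protocol's own 87% power and should not be used.

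**Conclusion.** The mismatch holds on the text alone, with no assumptions: objective and hypothesis on DOOR, inference only on DOOR/RADAR, components described but not tested.

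Its size is illustrative and rests on the assumptions in step 2 of the working. On those, a pure 25% DOT reduction moves DOOR/RADAR to about 0.52 to 0.53, significant in roughly one trial in five to one in three; a 40% reduction gives 0.54 to 0.56. None of this reflects a clinical gain.

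Moderate harm can be masked as neutral: 0.50 on DOOR/RADAR against 0.47 on DOOR. It is seldom declared significantly better at the planned effect. The rate is about 3% in the worked harm case, and 6% to 18% with 2 points of excess mortality as the only change. It becomes more common with larger DOT reductions. The documents do not support saying that the trial cannot see harm, or that it cannot answer its DOOR question at all, because the ranks and components are collected. As written, it does not plan to answer that question with an estimate and an interval.

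**What to change.** In Section 5.1 (secondary endpoints) and Section 9.4.1 (secondary analyses):
1. Add P(better DOOR) on the Table 3 ranks alone, ties counted half, with its 95% CI, as the analysis for the DOOR objective in Section 3.1.3.
2. State how antibiotic exposure enters DOOR/RADAR: which measure, over which window, and how it combines with rank. Use one label for it throughout.
3. Keep DOOR/RADAR as a separately labelled composite and always report it beside DOOR alone.
4. State that a claim of improved patient outcomes will not rest on DOOR/RADAR alone.

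The cost is wording plus one more run of an analysis already planned, on data already collected. The DOOR-alone estimate will probably lie nearer 50% than DOOR/RADAR.
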